• Introduction: Globally, osteoporosis poses a significant public health challenge, with an estimated 200 million patients affected worldwide and about it is responsible for nearly 9 million fractures annually, indicating its profound impact on morbidity, mortality, and healthcare costs [11]. In Bangladesh, the prevalence of osteoporosis is concerning, with a study revealing that among a cohort of 526 individuals, 37.3% are at risk of developing the condition [8]. The risk is notably higher in females (43.2%) compared to males (30.3%) and escalates with age, particularly after 50 years, reflecting global trends. Furthermore, the presence of diabetes and cardiovascular diseases significantly increases the risk, with a striking 78% of cardiovascular patients being at risk. Notably, individuals with multimorbidity present an even higher prevalence rate of 90%. This underlines an urgent need for effective screening and early detection strategies to mitigate the burden of osteoporosis, especially in resource-constrained settings.

Recent advancements in deep learning, particularly deep learning, have shown promise in utilizing plain radiographs for BMD prediction, potentially bypassing the need for more expensive and less accessible DEXA scans [12][13]. Studies leveraging CNNs have been successful in extracting clinically relevant features from X-ray images to predict BMD and assess fracture risk, demonstrating AI's potential in osteoporosis screening [14].

Despite these advancements, the application of AI in osteoporosis diagnosis faces challenges, notably the generalizability of models across diverse populations and healthcare settings. Most existing studies utilize datasets from localized patient populations and are often limited by the availability and quality of annotated data. This raises concerns about the models' performance and applicability in different regions, particularly in low- and middle-income countries where the disease burden is highest, and healthcare resources are scarce.

To address these gaps, our research aims to develop and evaluate an AI model for BMD prediction from X-ray images, with a particular focus on enhancing model generalizability and diagnostic accuracy. We intend to collect a comprehensive dataset comprising X-ray images, BMD measurements from local healthcare facilities. This diverse dataset will enable us to train and validate AI models that can robustly predict osteoporosis across different patient populations.

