Our goal is to create an AI-assisted diagnostic tool that can be easily integrated into clinical workflows, offering a cost-effective and accessible solution for osteoporosis screening.

• **Objectives:** The primary objective is to curate a comprehensive dataset of X-ray images sourced from publicly available domains and local health facilities, encompassing a diverse representation of patient demographics, geographic locations, and equipment variations. Building upon this dataset, we seek to develop a robust artificial intelligence model capable of prediction of bone mineral density from X-ray images.

The specific objectives of the study are:

- a) To develop a deep learning convolutional neural network (CNN) model that can accurately predict Bone Mineral Density (BMD) values from Xray images, using both prospective and retrospective data collection methods.
- b) To validate the AI model's performance on a diverse dataset encompassing a broad demographic, including variables such as age, gender, height, weight, menopausal status, and the presence of comorbidities like cardiovascular disease and diabetes.
- c) To evaluate the model's performance using a range of metrics, including Area Under the Precision-Recall Curve (AUPRC), accuracy, Mean Absolute Error (MAE), and Pearson Correlation Coefficient (PCC), ensuring its robustness in predicting BMD.
- d) To assess the usability and interpretability of the AI model's output by healthcare professionals, determining its integration into clinical practice and its impact on the diagnostic workflow efficiency.
- e) To measure the generalizability and adaptability of the model across various healthcare settings, ensuring the AI system's reliability on X-ray images from different populations and regions.

- f) To investigate the model's potential in enhancing early detection and treatment planning for osteoporosis by providing a non-invasive, cost-effective tool for BMD estimation, potentially leading to better patient management and outcomes.
- g) To assess the AI model's role as a decision support tool in determining the necessity for additional diagnostic procedures, such as DEXA scans, thereby optimizing patient care pathways and potentially reducing healthcare costs.

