 - a) **Study Population:** The study is structured as a prospective and retrospective investigation aimed at developing and evaluating an AI-based diagnostic tool for the prediction of BMD from X-ray image analysis. The population will include subjects with varying bone densities as determined by DEXA scans, which serve as the gold standard for BMD measurement. The study will target a diverse demographic to account for the variability in bone health across different ages, genders, and clinical backgrounds.

Inclusion criteria:

- Subjects of any gender and age group (18 and above) for whom X-ray imaging of relevant skeletal sites (e.g., spine, hip) is available.
- Individuals willing to participate and who have provided informed consent for the use of their X-ray images and clinical data for research purposes.
- Subjects with both X-ray images and DEXA scan results.
- Accessibility to supplementary medical records that may contribute to the model's predictive accuracy, such as historical data on fractures, calcium levels, and other osteoporosis-related factors.

Exclusion criteria:

- Subjects for whom X-ray images or clinical data are incomplete or of insufficient quality for analysis.
- Individuals with medical conditions that could significantly alter bone density independently of osteoporosis, such as bone cancers or certain metabolic diseases.
- Subjects who have undergone treatments or procedures that might significantly impact bone density measurement, such as long-term steroid use or recent orthopedic surgeries.
- Pregnant women, given the potential impact on screening results and the need for special considerations during pregnancy.
- b) **Sample size calculation:** Following the methodology of sample size calculation to evaluate diagnostic performance (for algorithms in this case), we use the following method of calculation for a target sensitivity and specificity incorporating disease prevalence [16]:

$$N_{sen} \ge \frac{Z^{2}_{(1-\alpha)/2} \times sen (1-sen)}{c^{2} \times p}$$

$$N_{spec} \ge \frac{Z^{2}_{(1-\alpha)/2} \times spec (1 - spec)}{c^{2} \times (1 - p)}$$

Where,

N _{sen}	=	Required sample size for sensitivity, sen
N_{spec}	=	Required sample size for specificity, spec
α	=	Confidence level
$Z^{2}_{(1-\alpha)/2}$	=	The Z -score for the confidence level α
p	=	Prevalence of osteoporosis
С	=	Precision
sen	_	
sen	=	Estimated sensitivity
spec	=	Estimated specificity

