The final sample size N is calculated based on the larger of the two values N_{sen} and N_{spec} . In this study, as we are using deep learning techniques, we need the medical image samples to reflect the various osteoporosis, osteopenia and normal cases. For our analysis, we assume an 95% confidence level, precision of 0.05, and prevalence of osteoporosis, p = 0.373 [8]. We estimate the sensitivity and specificity of our algorithms to be at 91.1% and 68.9% respectively (*sen* = 0.911 and *spec* = 0.689) [17]. Using these values, we obtain the sample size values: $N_{sen} = 335$ and $N_{spec} = 526$. Since $N_{spec} > N_{sen}$, the final sample size for the study will be:

$$N = N_{sen} = 526$$

We can set a target of N = 600.

c) **Procedures:** In the prospective phase of the study, data collection will be conducted within clinical settings. Eligible patients will be approached during X-ray scans and BMD tests and presented with a consent form for their consideration. Upon agreement, a unique identifier will be assigned to maintain data integrity while preserving patient anonymity. Following the consent process, patients will provide essential clinical information. Healthcare professionals will perform an X-ray or DEXA scan, and the results will be generated and collected. This approach ensures the acquisition of non-identifiable information, unique data identifiers, and informed consent directly within the clinical setting, aligning with the specific requirements of the study.

In the retrospective phase of the study, additional data will be extracted from the clinic's database. We will collect all spine and hip X-ray images and BMD reports from the radiology department. The identification and matching process will rely on patient ID, phone number, date of birth, and other shared clinical information present in both the X-ray and BMD reports. Given the retrospective nature of this approach, tracking down and obtaining consent from individual patients is not feasible. To address privacy concerns, any personally identifiable patient information will be systematically removed from the collected data. This strategy ensures compliance with privacy standards while utilizing valuable information from previous screenings. Although informed consent cannot be obtained for this specific dataset, the study will strictly adhere to ethical guidelines and prioritize patient privacy throughout the data extraction process from the clinic's database.

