f) Statistical Analysis: Upon finalizing the dataset, our statistical analysis will concentrate on evaluating the artificial intelligence model's capability to predict BMD from X-ray images accurately. Performance metrics such as Mean Absolute Error (MAE), Pearson Correlation Coefficient (PCC), Area Under the Precision-Recall Curve (AUPRC), and accuracy will be employed to meticulously assess the model's performance. To ensure the reliability of our findings, we will implement k-fold cross-validation techniques, providing a framework for evaluating our model across various subsets of data. This approach will allow us to calculate mean values and standard deviations for each performance metric, offering a comprehensive understanding of the model's predictive accuracy and consistency. The culmination of our analysis will involve a comparative review of different CNN architectures and training methodologies to determine the most effective strategy for BMD prediction from X-ray images.

Utilization of Results: The study results will play a crucial role in the development and evaluation of an automatic BMD prediction algorithm for osteoporosis screening. The algorithm's primary objectives are:

a) BMD Prediction: To accurately predict BMD values from X-ray images, facilitating an automated assessment tool for early detection of osteoporosis and osteopenia. This tool aims to bridge the gap in accessibility to BMD testing, especially in resource-limited settings.

b) Clinical Decision Support: To aid healthcare professionals by providing automated BMD assessments, enhancing their ability to make informed decisions regarding patient care. The model's predictions can help prioritize patients who need further testing or intervention, streamlining the diagnostic process.

c) Correlation Analysis: To explore and identify significant relationships between BMD or osteoporosis and collected clinical covariates such as age, gender, menopausal status, cardiovascular diseases, and diabetes. This analysis aims to enhance understanding of the factors influencing bone health, contributing to personalized and more precise osteoporosis risk assessment and management strategies.

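### The sample size rests on the precision of sensitivity and specificity, but neither is named among the performance results, and a fold SD is not the 95% interval on which N was based.

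*Protocol*

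**What the plan says.** Methodology b) Sample size calculation states that "we use the following method of calculation for a target sensitivity and specificity incorporating disease prevalence". The inputs are 95% confidence, "precision of 0.05, and prevalence of osteoporosis, p = 0.373", and the expected performance: "We estimate the sensitivity and specificity of our algorithms to be at 91.1% and 68.9% respectively". The rule is that "The final sample size N is calculated based on the larger of the two values". The results are 335 for sensitivity and 526 for specificity, so 526 is taken. The target is then set at 600 with no further calculation shown.

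Methodology f) Statistical Analysis states that "Performance metrics such as Mean Absolute Error (MAE), Pearson Correlation Coefficient (PCC), Area Under the Precision-Recall Curve (AUPRC), and accuracy will be employed". It adds k-fold cross-validation (k not given), a mean and standard deviation for each metric, and a comparison of CNN architectures and training methods to find the best one. Objective c lists the same four metrics. Sensitivity and specificity as study measures appear only in the sample size section.

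The Rationale and objective g give the intended use: a first assessment that helps physicians decide whether a DEXA scan is needed.

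**The concern.** A precision-based sample size is a statement about the width of an interval for a particular result. Here the protocol fixes that result in one section and names different results in two others. If the report kept to the named metrics, no reader could check it against the 91.1%, the 68.9% or the ±0.05 that justify 600 patients.

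The intended use makes this more than bookkeeping. Triage to DEXA has two separate errors: an osteoporosis case not referred, and a patient without osteoporosis referred needlessly. MAE and the Pearson correlation describe the continuous prediction. Accuracy adds the two errors together. AUPRC is built from precision and recall; recall is sensitivity, but the area averages over cut-offs and does not use specificity, which is the measure that set N. The form of summary also differs: a standard deviation across folds describes how much folds vary and is not a 95% confidence interval.

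**Working it through.** **Inputs.** From the sample size section: z = 1.96, precision 0.05, prevalence 0.373, sensitivity 0.911, specificity 0.689, target N = 600.

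**1. The plan's own figures.**
- Sensitivity: 1.96² × 0.911 × 0.089 / (0.05² × 0.373) = 334.0, rounded up to 335.
- Specificity: 1.96² × 0.689 × 0.311 / (0.05² × 0.627) = 525.2, rounded up to 526.

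Both reproduce. The 526 comes wholly from the specificity criterion.

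**2. Precision at the target.** At N = 600 and prevalence 0.373 there are 600 × 0.373 = 223.8 cases and 376.2 non-cases.
- Sensitivity half-width: 1.96 × √(0.911 × 0.089 / 223.8) = 0.037.
- Specificity half-width: 1.96 × √(0.689 × 0.311 / 376.2) = 0.047.

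Both are within ±0.05 on the protocol's assumptions.

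**3. What accuracy hides.** Assume that accuracy means osteoporosis yes/no; the protocol does not say this, and its Data Interpretation section speaks of three categories.
- Planned values: 0.373 × 0.911 + 0.627 × 0.689 = 0.772.
- Hypothetical sensitivity 0.60: the same accuracy needs specificity (0.7718 − 0.373 × 0.60) / 0.627 = 0.874.
- Errors per 600, planned values: 223.8 × 0.089 = 19.9 missed and 376.2 × 0.311 = 117.0 needlessly flagged, 136.9 in total.
- Errors per 600, hypothetical values: 223.8 × 0.40 = 89.5 missed and 376.2 × 0.126 = 47.4 flagged, again 136.9.

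The accuracy is identical, with about 20 missed cases in one and 90 in the other.

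**4. Fold SD against the 95% interval.** Take specificity 0.689 at N = 600 and consider sampling variation alone. With an assumed 5 folds, each holds 376.2 / 5 = 75.2 non-cases and the expected SD across folds is about √(0.689 × 0.311 / 75.2) = 0.053. With 10 folds it is √(0.689 × 0.311 / 37.6) = 0.075. The half-width in step 2 is 0.047 in both cases. The fold SD moves with the choice of k and cannot be read against ±0.05.

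**5. Case counts that ±0.05 needs.** If sensitivity and specificity are exactly 0.911 and 0.689:
- Cases: 1.96² × 0.911 × 0.089 / 0.05² = 124.6, so at least 125.
- Non-cases: 1.96² × 0.689 × 0.311 / 0.05² = 329.3, so at least 330, which leaves at most 600 − 330 = 270 cases.
- Prevalence range at N = 600: 125/600 = 0.21 to 270/600 = 0.45.

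The range shifts with other values. With an assumed sensitivity of 0.85, 1.96² × 0.85 × 0.15 / 0.05² = 195.9, so 196 cases and a range of about 0.33 to 0.45. With an assumed specificity of 0.80 (sensitivity as planned), 1.96² × 0.80 × 0.20 / 0.05² = 245.9, so 246 non-cases and a range of about 0.21 to 0.59.

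The sample's prevalence is uncertain. The Introduction describes the source of the 37.3% thus: "among a cohort of 526 individuals, 37.3% are at risk of developing the condition". Being at risk need not equal DEXA-defined osteoporosis among patients who had both examinations.

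**The case against.** Both metric lists are open: objective c uses *including* and section f uses *such as*. The sample size section and Ethical Implications both state an aim of evaluating diagnostic performance, and Data Collection makes the standard test result the ground truth. Sensitivity and specificity can therefore be computed from the planned data, and nothing rules them out. That stands. A reader might infer that the protocol excludes them or that they will go unreported, and the text does not support this.

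A reader might also infer that 600 is too few. The documents do not support that either. On the protocol's inputs both measures fall within ±0.05 at 600, and two-class accuracy would need only 1.96² × 0.772 × 0.228 / 0.05² ≈ 271 patients for ±0.05. Nor can a further reason for 600 be ruled out: the consent waiver justification refers to a sample size section on overfitting that does not appear in the available text.

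Finally, a cut-off, an interval method and the pooling of folds are details often left to an analysis plan, which may exist. Their absence alone would be no finding. What remains is internal to the protocol: it states its sizing criterion, names its metrics twice, and the two do not match.

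**Conclusion.** The point holds as a mismatch between the sizing criterion and the named results. N = 526 is correctly calculated, but from two measures that neither objective c nor section f names, and the planned summary is not the interval on which the calculation rests. The harm is in reporting: results limited to the four named metrics could not show whether ±0.05 was met or how many osteoporosis cases the tool misses. The size of the gap (20 against 90 missed cases per 600 at 77.2% accuracy) rests on two-class accuracy, prevalence 0.373 and a hypothetical comparator.

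The 125 to 270 case range should not be read as a general pass or fail limit for the study. It applies only at sensitivity 91.1% and specificity 68.9%. The point should be fixed before the data are analysed, but it does not invalidate the design.

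**What to change.** - **Objective c and section f.** Name sensitivity and specificity for DEXA-defined osteoporosis at a pre-stated cut-off on predicted BMD, with 95% confidence intervals from one out-of-fold prediction per patient. Keep the four present metrics, and keep the fold SDs as a descriptive measure of stability.
- **Protection from selection.** Take the out-of-fold predictions from nested cross-validation, or from an architecture fixed beforehand, so that the planned architecture comparison does not make them optimistic. The architecture could be fixed in the initial step on public data shown in the Flow Chart, if those images carry BMD labels, which the protocol does not say.
- **Sample size section.** State that, only if sensitivity and specificity are 91.1% and 68.9%, ±0.05 on both at N = 600 needs 125 to 270 osteoporosis cases (prevalence about 0.21 to 0.45). State that the range shifts with other values, for example to about 0.33 to 0.45 if sensitivity is 0.85, and that the actual case counts and intervals will be reported.

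**Cost.** Protocol wording and a few lines of analysis code. Nesting adds computing: with K architectures and an assumed 5 outer and 5 inner folds, 25K + 5 training runs instead of 5K, so 80 instead of 15 for three architectures. Fixing the architecture early avoids this, at the risk that it is not the best one on local images. On the protocol's own assumptions no extra patients are needed.

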- d) **Methods of Data Collection:** The following fields will be recorded in the data collection for this study:
 - Patient ID (unique identification number)
 - Date & time of the data input
 - Age
 - Gender
 - Phone number
 - X-ray image (hip or spine)

- DEXA scan result
- BMI
- Menopausal status
- Diabetes
- Cardiovascular disease and other clinical covariates

The X-ray images, and DEXA scan result of the subjects along with the relevant clinical covariates will be used to design the algorithms. The standard test status and the corresponding result will be used as the ground truth for our detection algorithm.

e) **Data Interpretation:** Upon the conclusion of data collection, exploratory data analysis to assess the distribution of patients across different demographics and clinical factors, including age, gender, menopausal status, presence of cardiovascular diseases, diabetes, and their correlation with BMD values. This process will ensure a comprehensive understanding of the dataset's characteristics and the establishment of a balanced dataset that represents a wide spectrum of patient profiles.

The refined dataset will serve as the foundation for training and evaluating our AI model, specifically designed for the regressionbased prediction of BMD from X-ray images. Our AI algorithm will leverage CNN to process X-ray images and predict BMD values, aiming to identify potential cases of osteopenia, osteoporosis, and normal.

To ascertain the model's performance and its clinical applicability, we will compare the AI-generated predictions with actual BMD measurements obtained from DEXA scans. This validation process will involve collaboration with orthopedic specialists and radiologists who will review the AI predictions in the context of their clinical experience and available patient information.

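### None of the four named metrics shows signed error or error at low BMD, and the sensitivity and specificity that size the study are not among them

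*Protocol*

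**What the plan says.** Methodology, f) Statistical Analysis, assesses the model by "Performance metrics such as Mean Absolute Error (MAE), Pearson Correlation Coefficient (PCC"), AUPRC and accuracy. Objectives, item c), names the same four: "Area Under the Precision-Recall Curve (AUPRC), accuracy, Mean Absolute Error (MAE), and Pearson Correlation Coefficient (PCC), ensuring its robustness in predicting BMD". In the analysis section the list is introduced as examples, so it is not closed.

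Methodology, e) Data Interpretation, describes a regression network that will "predict BMD values, aiming to identify potential cases of osteopenia, osteoporosis, and normal". It adds that "we will compare the AI-generated predictions with actual BMD measurements obtained from DEXA scans", without naming an agreement statistic.

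Back in f), k-fold cross-validation is used to "calculate mean values and standard deviations for each performance metric", and the analysis ends in a "comparative review of different CNN architectures and training methodologies to determine the most effective strategy for BMD prediction". The metrics therefore bear on model choice as well as on the final claim.

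Methodology, b) Sample size calculation, rests on sensitivity 0.911 and specificity 0.689, with precision 0.05 and prevalence 0.373. Neither sensitivity nor specificity appears in either list of metrics.

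**The concern.** Only MAE and PCC measure agreement on the BMD value itself. PCC is unchanged if every prediction is shifted or compressed. MAE does rise under a large uniform shift, but it has no sign, it averages over all participants, and it is lowered by shrinking predictions towards the mean. Neither says where on the BMD scale the error lies.

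The two classification metrics do not fill the gap. AUPRC computed on predicted BMD depends on rank order only. Accuracy weighs missed cases and false alarms together, so a fall in sensitivity can be offset by a rise in specificity.

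The Rationale gives the tool the job of guiding whether a DEXA scan is warranted. Over-prediction at low BMD falls on the patients it is meant to find. With these metrics alone, the study could report accurate BMD prediction, and prefer one architecture over another, without showing that error.

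**Working it through.** **1. The plan's own figure.** With z = 1.96:
- N for sensitivity = 1.96² × 0.911 × 0.089 / (0.05² × 0.373) = 334.02, rounded up to 335.
- N for specificity = 1.96² × 0.689 × 0.311 / (0.05² × 0.627) = 525.15, rounded up to 526.

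Both match the protocol. The study is sized to estimate two quantities that its metric lists omit.

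**2. Illustration: inputs.** From the protocol: osteoporosis share p = 0.373. Assumed, because the protocol gives no figure or rule:
- true and predicted BMD are bivariate normal, in SD units of true BMD;
- the prediction is the least-squares predictor, with zero overall bias and SD equal to r, the PCC;
- r lies between 0.7 and 0.9;
- the DEXA cut c is applied unchanged to predicted BMD.

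The cut is c = z(0.373) = −0.324.

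**3. Formulas.**
- MAE = √(1 − r²) × √(2/π). Predicting the mean for everyone gives √(2/π) = 0.798 SD.
- Mean over-prediction in the osteoporosis group = (1 − r²) × φ(c)/p, where φ(c)/p = 0.3786/0.373 = 1.015.
- Sensitivity = P(predicted < c and true < c)/p.
- Specificity = 1 − P(predicted < c and true ≥ c)/(1 − p).
- Accuracy (osteoporosis or not) = p × sensitivity + (1 − p) × specificity.

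At r = 0.7:
- MAE = 0.714 × 0.798 = 0.57 SD, 29% below mean-only prediction.
- Over-prediction = 0.51 × 1.015 = 0.52 SD.
- Accuracy = 0.373 × 0.614 + 0.627 × 0.852 = 0.76.

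| PCC | MAE (SD) | Over-prediction in osteoporosis (SD) | Sensitivity | Specificity | Accuracy | Specificity if the cut is moved to sensitivity 0.911 |
|---|---|---|---|---|---|---|
| 0.7 | 0.57 | 0.52 | 0.61 | 0.85 | 0.76 | 0.52 |
| 0.8 | 0.48 | 0.37 | 0.70 | 0.87 | 0.81 | 0.64 |
| 0.9 | 0.35 | 0.19 | 0.80 | 0.90 | 0.86 | 0.80 |

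Overall bias is zero in every row.

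**4. What each metric registers, at PCC 0.8.**
- Add 0.5 SD to every prediction: PCC stays at 0.80 and AUPRC at 0.828. MAE goes from 0.48 to 0.64 SD, and sensitivity from 0.70 to 0.37.
- Add 0.3 SD: sensitivity goes from 0.70 to 0.50 and specificity from 0.87 to 0.95, while accuracy moves only from 0.81 to 0.78.
- Compare the shrunken predictor with an unshrunken one (slope 1 on true BMD) of the same PCC. MAE is 0.48 against 0.60 SD, sensitivity 0.70 against 0.77, specificity 0.87 against 0.82, and accuracy 0.81 against 0.80. The two rank patients equally well. MAE prefers the one that misses more cases at the fixed cut.

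**5. A lower share.** With an assumed osteoporosis share of 0.15, sensitivity is 0.30, 0.46 and 0.65 at PCC 0.7, 0.8 and 0.9. Accuracy at PCC 0.7 is 0.87, while labelling everyone negative would give 1 − 0.15 = 0.85.

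**The case against.** **The list is open and longer than two.** A reader might infer that BMD agreement, or the model as a whole, is to be judged by PCC and MAE alone. The protocol does not say so: AUPRC and accuracy are named beside them, and the wording leaves room for more. What stands is that neither added metric shows the direction or location of error on the BMD scale, and that both lists omit signed error, sensitivity and specificity.

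**Much of the gap is threshold position or discrimination.** This largely stands. At the DEXA cut, the illustrated specificity (0.85 to 0.90) is well above the planning 0.689. Moving the cut to reach sensitivity 0.911 leaves specificity at 0.52 and 0.64 at PCC 0.7 and 0.8, below 0.689; only at 0.9 (0.80) are both planning values met. Limited discrimination at PCC 0.7 to 0.8 is something PCC and AUPRC do reveal. Nor are accuracy 0.76 and MAE 0.57 SD at PCC 0.7 plainly good results, and the protocol sets no threshold for any metric.

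**The rule and the shrinkage are assumed.** This also stands. The protocol does not say that the DEXA cut will be applied to predicted BMD, and it gives no loss function and no expected PCC. Some over-prediction among patients with low true BMD is inherent in any least-squares predictor with PCC below 1, so finding it would not by itself show a badly fitted model. Its size still matters for a screening use.

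**This is detail for an analysis plan.** Limits of agreement and the choice of cut are often left there, and a plan not shown may add them. However, the protocol states its metrics twice and ties the evaluation to architecture choice, so the gap is best closed in its own text.

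**Conclusion.** The point holds as a gap in the named metrics. MAE and PCC are reasonable but incomplete for this purpose, and AUPRC and accuracy do not complete them. As written, the evaluation could support a claim of accurate BMD prediction, and help select an architecture, without showing over-prediction at low BMD and without reporting the two quantities that size the study.

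In the illustration the over-prediction in the osteoporosis group runs from 0.19 SD at PCC 0.9 to 0.52 SD at PCC 0.7, with sensitivity from 0.80 down to 0.61 and specificity from 0.90 down to 0.85. These figures rest on normality, a least-squares predictor, zero overall bias, a share of 0.373 and the unstated DEXA-cut rule.

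A reader might infer that the tool will fall short of a required sensitivity of 0.911. The documents do not support that: 0.911 is a planning estimate, not a performance target, and nothing in the protocol predicts the sensitivity that will be achieved.

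**What to change.** In Methodology, f) Statistical Analysis, with a matching change to Objectives item c):

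- Make mean signed error (predicted minus DEXA) with 95% limits of agreement the agreement result, overall and within each DEXA category (normal, osteopenia, osteoporosis). Keep PCC as description only.
- Report sensitivity and specificity for osteoporosis together, with 95% confidence intervals, in the held-out folds. Fix any cut on predicted BMD inside the training folds, and state the rule for choosing it.
- Use these results alongside MAE when comparing architectures.

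The cost is a little more analysis on data already to be collected, with no change in sample size. Results may look less favourable than the present four metrics alone.
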